8.7 Efficacy Subgroup Analyses

To evaluate the consistency of the efficacy over demographic and other baseline characteristics, subgroup analysis will be performed for the co-primary endpoints for the subgroups listed in [Table 1](#) below using ITT1A.

For efficacy subgroup analysis, point estimate and 95% CI for each treatment group as well as point estimate and 95% CI for treatment differences between each risankizumab group and the placebo group will be presented. No p-value will be provided. If any of the resulting subgroups except for age, sex and race has fewer than 10% of the planned study size, the subgroup analyses for that category will not be presented.

Table 1. Subgroups for Efficacy Analysis

| Subgroup Factor | Categories |
|--|---|
| Age | < 18, [18, 40), [40, 65), ≥ 65 |
| Sex | Male or Female |
| Weight | < 60 kg or ≥ 60 kg |
| Race | White or non-White |
| Geographic Region | North America, South/Central America, Western Europe, Eastern Europe, Asia, Other |
| Prior Biologics Failed | Yes or No, if Yes, please analyze (1, > 1) |
| Prior Ustekinumab Failure (within bio-IR population) | Yes or No |
| Prior TNF Failure (within subjects with Prior TNF Failure) | 1, >1 |
| Prior Vedolizumab Failure (within bio-IR population) | Yes or No |
| Baseline Steroids Use | Yes or No |
| Baseline Immunodulator Use | Yes or No |
| Baseline CDAI | ≤ median or > median |
| Baseline CDAI | ≤ 300 or > 300 |
| Baseline SF | ≤ median or > median |
| Baseline AP Score | ≤ median or > median |
| Baseline SES-CD | ≤ median or > median |
| Baseline SES-CD | ≤ 15 or > 15 |
| Disease Duration at Baseline | ≤ median or > median |
| Disease Duration at Baseline | ≤ 5 years or > 5 years |
| Baseline hs-CRP | ≤ median or > median |
| Baseline hs-CRP | ≤ 5 mg/L or > 5 mg/L |
| Baseline Calprotectin | ≤ median or > median |
| Baseline Calprotectin | ≤ 250 mg/kg or > 250 mg/kg |
| Crohn's Disease Location at Baseline | Colonic only, Ileal only, Ileal-colonic |

9.0 Safety Analyses

9.1 General Considerations

Safety analyses will include reporting of adverse events, laboratory, and vital signs measurements by treatment group, including a total group for all subjects on

risankizumab. All safety analyses will be performed for the 12-Week Induction Period at the time of database lock. The separate safety analysis for subjects who received at least one dose of risankizumab during the Induction Period 2 will be performed.

The following summary statistics will be presented for subjects who have both baseline and post-baseline values for laboratory parameters and vital signs: the mean value at baseline and at each respective protocol specified visit, and the mean, standard deviation and median for changes from baseline. Categorical data will be summarized using frequencies and percentages. The risk difference and 95% CI between each risankizumab group and placebo group will be presented for safety analysis.

For the safety analysis, subjects are assigned to a treatment group based on the treatment actually received, regardless of the treatment randomized.

For the 12-Week Induction Period analysis, the baseline for safety analysis is defined as the last available measurement before study drug administration for all subjects. For the Induction Period 2 analysis, the baseline for safety analysis will be the last available measurement before the first dose of risankizumab administration in Induction Period 2.

Missing safety data will not be imputed.

9.2 Adverse Events

Adverse events (AEs) will be summarized and presented using primary MedDRA System Organ Classes (SOCs) and preferred terms (PTs) according to the version of the MedDRA coding dictionary used for the study at the time of database lock. The actual version of the MedDRA coding dictionary used will be noted in the AE tables and in the clinical study report. Specific adverse events will be counted once for each subject for calculating percentages, unless stated otherwise. In addition, if the same adverse event occurs multiple times within a subject, the highest severity and level of relationship to investigational product will be reported.

9.2.1 Treatment-Emergent Adverse Events

12-Week Induction Period: Treatment emergent AEs (TEAEs) for the 12-Week Induction Period are defined as events that begin either on or after the first dose of the study drug in the 12-Week Induction Period and until the first dose of study drug in the Study M16-000 if the subject is enrolled into the Study M16-000 or until first dose of study drug in Induction Period 2 if the subject is enrolled into Induction Period 2, or within 140 days after the last dose administration of the study drug in 12-Week Induction Period if the subject does not participate in the Study M16-000 or the Induction Period 2.

Induction Period 2: Treatment-emergent AEs (TEAEs) for the Induction Period 2 are defined as events that begin either on or after the first dose of the study medication in the Induction Period 2 and until first dose of study drug in the Study M16-000 if the subject is enrolled into the Study M16-000 or within 140 days after the last dose of the study drug in the Induction Period 2 if the subject does not participate in the Study M16-000.

All Risankizumab: Treatment-emergent AEs (TEAEs) for "All Risankizumab" are defined as events that begin either on or after the first dose of risankizumab and until first dose of study drug in the Study M16-000 if the subject is enrolled into the Study M16-000 or within 140 days after the last dose of risankizumab in the study if the subject does not participate in the Study M16-000.

Events where the onset date is the same as the study drug start date are assumed to be treatment-emergent, unless the study drug start time and the adverse event start time are collected and the adverse event start time is prior to the study drug start time. If an incomplete onset date was collected for an adverse event, the event will be assumed to be treatment-emergent unless there is other evidence that confirms that the event was not treatment-emergent (e.g., the event end date was prior to the study drug start date).

All treatment-emergent AEs will be summarized overall, as well as by primary MedDRA SOC and Preferred Term. The SOCs will be presented in alphabetical order, and the PTs will be presented in alphabetical order within each SOC.

The number and percentage of subjects experiencing treatment-emergent AEs will be summarized. The risk difference and 95% CI between each risankizumab group and placebo group will be presented.

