2.2 Study Design Overview

This is a Phase 3, multicenter, randomized, double-blind, placebo-controlled study designed to evaluate the efficacy and safety of risankizumab as an induction therapy in subjects with moderately to severely active CD.

The study consists of the following periods:

1. Screening period of up to a maximum of 35 days
2. 12-week randomized, double-blinded IV therapy induction period (12-Week Induction Period)
3. 12-week randomized, double-blinded, double-dummy Induction Period 2 (Induction Period 2) for subjects who do not achieve clinical response at Week 12
4. 20-week follow up period from the last dose of study drug.

The schematic of the study is shown in [Figure 1](#).

Figure 1. Study Schematic

[figure not shown]
[figure not shown]

Figure 1. Study Schematic (Continued)

DC = discontinued; IR = subjects with inadequate clinical response to induction; IV = intravenous; R = subjects with clinical response; RR = re-randomize

Approximately 855 patients with moderate to severe CD who had baseline eligible SES-CD (eligible SES-CD is defined as total SES-CD score excluding presence of narrowing subscore) of ≥ 6 (≥ 4 for isolated ileal disease) are to be randomized in a ratio of 2:2:1 to one of the three following treatment groups in the 12-Week Induction Period.

- Placebo IV (n = 342)
- Risankizumab 600 mg IV (n = 342)
- Risankizumab 1200 mg IV (n = 171)

In addition to the 855 subjects, up to 85 subjects with a lower SES-CD, defined as an eligible SES-CD of ≥ 3 to < 6 for ileocolonic or colonic disease or SES-CD of 3 for isolated ileal disease will be enrolled in order to inform treatment effect in this patient population, but these subjects will not be included in the primary ITT population for efficacy analysis.

Each treatment group receives the corresponding dose of risankizumab or placebo IV infusion at Week 0, Week 4, and Week 8. At Week 12, patients are evaluated for clinical response, defined as $\geq 30\%$ decrease in average daily SF and/or $\geq 30\%$ decrease in average daily AP score and both not worse than baseline.

Visits for clinical evaluation will occur at baseline/Week 0, Weeks 4, 8, and 12 or Premature Discontinuation (PD).

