Subjects, who do not achieve clinical response at Week 12 will be randomized by Interactive Response Technologies (IRT) to the Induction Period 2, a double-blind, double dummy 12-week treatment period. Subjects who received risankizumab induction treatment during the 12-Week Induction Period will be randomized 1:1:1 to:

- Risankizumab 1200 mg IV
- Risankizumab 360 mg subcutaneous (SC)
- Risankizumab 180 mg subcutaneous (SC)

Subjects who received placebo induction treatment during the 12-Week Induction Period will receive:

- Risankizumab 1200 mg IV

The IV risankizumab dose or matching IV placebo will be given at Weeks 12, 16, and 20; The SC risankizumab dose or matching SC placebo will be given at Weeks 12, and 20.

At Week 24, subjects who participated in the blinded Induction Period 2 will be reassessed and undergo a third endoscopy for evaluation of mucosal inflammation. Subjects who achieve clinical response at Week 24 may be eligible to enter the Study M16-000. Subjects without clinical response at Week 24, as well as all subjects who are terminated the study early (including subjects who are eligible for but do not participate in the blinded Induction Period 2), will be discontinued and have a follow-up call 140 days

from the last dose of study drug to obtain information on any new and/or ongoing adverse events (AEs).

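### Treatment-emergent AE risk differences against placebo in the 12-Week Induction Period are crude percentages over windows of about 84 days for continuers and 140 to 196 days for others

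*SAP*

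**What the plan says.** SAP Section 9.2.1 gives three possible ends to the treatment-emergent window of the 12-Week Induction Period:

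- "until the first dose of study drug in the Study M16-000 if the subject is enrolled into the Study M16-000";
- "until first dose of study drug in Induction Period 2 if the subject is enrolled into Induction Period 2";
- for everyone else, "or within 140 days after the last dose administration of the study drug in 12-Week Induction Period if the subject does not participate" in either.

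Section 2.2 supplies the calendar. "Each treatment group receives the corresponding dose of risankizumab or placebo IV infusion at Week 0, Week 4, and Week 8". Induction Period 2 starts at Week 12: "The IV risankizumab dose or matching IV placebo will be given at Weeks 12, 16, and 20". Follow-up is a "20-week follow up period from the last dose of study drug". Clinic visits fall at Weeks 4, 8 and 12 or at premature discontinuation (PD). Subjects who terminate early, including those eligible for Induction Period 2 who do not enter it, "will be discontinued and have a follow-up call 140 days" after the last dose.

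The comparison with placebo is fixed in Section 9.2.1: "The risk difference and 95% CI between each risankizumab group and placebo group will be presented". Section 9.1 applies this to the safety analysis generally, and Section 9.2.6 repeats it for the areas of safety interest.

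Exposure-adjusted rates are also planned: for the AE overview (9.2.2), all TEAEs (9.2.4), SAEs (9.2.5) and areas of safety interest (9.2.6). Their denominator in Section 9.2.4 runs to the last dose plus 140 days or the next period's first dose, whichever is earlier. A rate censored at the first event is optional and limited to deaths and selected categories. Under Sections 8.1 and 9.1, the 12-week data are locked and the safety analyses run once all subjects have completed Week 12 or PD.

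**The concern.** A percentage of subjects with an event depends on how long each subject is watched. Here that time is set by something that happens after randomisation: whether the subject goes on to the next period or study. If more placebo than risankizumab subjects fail to continue, the placebo arm has a longer average window. It then collects more subjects with events even when the true hazards are identical, and the crude risk difference makes risankizumab look safer than it is. If more risankizumab subjects fail to continue, the sign reverses.

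The estimates affected are the only AE contrasts with placebo for which the SAP states a CI, so they are the ones readers will rely on. The exposure-adjusted rates are the natural corrective, but as specified they cannot fully play that part.

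**Working it through.** **Windows, from the SAP.**
- 20 weeks × 7 = 140 days, which reproduces the 140 days of Section 9.2.1.
- Continuing subject: 12 × 7 = 84 days. For M16-000 this assumes a first dose at about Week 12; for Induction Period 2, Section 2.2 states Week 12.
- Subject who enters neither: last dose on Day 0, 28 or 56, plus 140 = Day 140, 168 or 196.
- Largest ratio: 196 / 84 = 2.33.

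**Inputs the SAP does not give (assumptions).** Share not continuing: *q* = 8% on risankizumab and 15% on placebo. Twelve-week AE risk: *r* = 10% or 55%. The hazard is constant, equal in both arms and unchanged after Day 84. Every non-continuer has the 196-day window.

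**Spurious crude risk difference.** Risk over *w* days is R(*w*) = 1 − (1 − *r*)^(*w*/84). An arm's crude risk is (1 − *q*)·*r* + *q*·R(*w*), so the difference between arms is (0.08 − 0.15) × [R(*w*) − *r*].

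Full capture of the tail uses *w* = 196. Half capture of the 112 tail days is modelled as half the hazard, equivalent to 56 extra days, so *w* = 140. That also equals full capture when every non-continuer stopped after the first dose.

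| 12-week risk | Tail capture | R(*w*) | Spurious difference |
|---|---|---|---|
| 10% | full | 1 − 0.90^(196/84) = 21.8% | −0.07 × 11.8 = −0.8 points |
| 10% | half | 1 − 0.90^(140/84) = 16.1% | −0.07 × 6.1 = −0.4 points |
| 55% | full | 1 − 0.45^(196/84) = 84.5% | −0.07 × 29.5 = −2.1 points |
| 55% | half | 1 − 0.45^(140/84) = 73.6% | −0.07 × 18.6 = −1.3 points |

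With equal shares the first factor is zero, and so is the bias. With one common cut-off for all subjects, R(*w*) = *r* and the bias is again zero under equal hazards.

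**Scale.** With the 342 and 171 subjects of Section 2.4, the 95% CI half-width is 1.96 × √[*r*(1 − *r*)(1/342 + 1/171)]: about 5.5 points at 10% and 9.1 points at 55%.

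**Exposure-adjusted rates.** The relative observed rate in an arm is (84 + 112·*q*·*c*) / (84 + 112·*q*), where *c* is the share of tail events captured.
- Full capture (*c* = 1): the factor is 1 in both arms, so there is no bias.
- Half capture: 88.48 / 92.96 = 0.952 on risankizumab and 92.4 / 100.8 = 0.917 on placebo, a rate ratio of 0.952 / 0.917 = 1.04.

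This runs in the opposite direction to the crude bias.

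The lock makes incomplete capture likely for some subjects. A non-continuer whose last dose was on Day 56 and whose Week 12 visit closes the database has 84 − 56 = 28 of the 140 days behind them. The other 112 days are credited in the denominator as written but cannot contribute events.

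**The case against.** Several stronger readings are tempting, and the document does not support them.

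- **That the window in the placebo comparison depends on efficacy response.** It does not do so directly. Week 12 non-responders go to Induction Period 2, and Section 9.2.1 also provides for direct entry to M16-000; either route gives the short window. Only stopping early or not continuing lengthens it. Response at Week 24 does govern eligibility for M16-000, but Induction Period 2 has no placebo arm. There the point affects only how dose-group percentages are read.
- **That 196 days rest on one telephone call.** The call covers only the tail after the Week 12 or PD visit, and the protocol, not shown, may add contacts.
- **That unequal time is ignored.** Four sections plan exposure-adjusted rates whose denominator follows the same window.
- **That the comparison is known to favour risankizumab.** The SAP gives no non-continuation share by arm, so neither the sign nor the size is known. Giving every non-continuer 196 days and full capture is the high end of the calculation. Tails cut short by the lock would reduce the crude bias further.
- **That percentages in the two induction periods are misleadingly set side by side.** The SAP plans a separate analysis for Induction Period 2, not that comparison.

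A fair defence of the 140-day window also stands. It matches the 20-week follow-up and the death categories in Section 9.2.2, and cutting at the next first dose is reasonable because treatment may change there. Replacing that presentation would move late serious events in subjects who stopped out of the headline tables. This argues for an added analysis, not a substitute.

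The defence does not supply a placebo contrast with a CI over a fixed time.

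**Conclusion.** The point holds in limited form. In the 12-Week Induction Period, the risk differences with CI against placebo rest on windows of about 84 days for continuers and 140 to 196 days for others, decided by a post-randomisation event. They are biased to the extent that non-continuation differs by arm, and unbiased in this respect if it does not.

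The figures in the table depend on assumed shares, constant equal hazards and a maximal window. They are small beside the sampling error at these arm sizes, but systematic: they shift the estimate without widening its interval.

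The planned rates do not settle the matter. They carry no stated between-arm CI, the first-event version is optional, and their denominator may include unobserved time, which pushes the error the other way. A cheap improvement is justified; nothing here shows that the safety conclusions would be wrong.

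**What to change.** 1. Keep the 140-day tables as planned.
2. In Sections 9.2.1, 9.2.2, 9.2.5 and 9.2.6, add percentages, risk differences and 95% CIs over a common window for the AE overview, SAEs and areas of safety interest. The window runs from first dose to the earlier of Day 84 and the first dose of the next period or study.
3. Tabulate later events, up to the end of the existing window, separately so that none is lost.
4. In Section 9.2.4, end each subject's denominator at the last day actually observed, no later than the data cut-off for the lock.

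The cost is SAP wording, one analysis flag, a revised end date for exposure and a few extra tables, all from data already collected. Continuers whose next dose falls after Day 84 will have a few events in the later table. A common window equalises nominal time, not the completeness of reporting in subjects who withdraw before Day 84; a footnote should say so.

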2.3 Treatment Assignment and Blinding

At baseline, eligible patients will be randomized to three parallel groups with 1200 mg IV and 600 mg IV dose of risankizumab treatments or placebo in a 2:2:1 ratio. The 12-Week Induction Period randomization will be stratified by number of prior biologics failed (0, 1, > 1), baseline steroid use (Yes, No), and baseline eligible SES-CD (original, alternative), where the stratum of "original" includes the patients with baseline eligible SES-CD of ≥ 6 (or ≥ 4 for subjects with isolated ileal disease), and the stratum of "alternative" includes the patients with baseline eligible SES-CD of ≥ 3 to < 6 for ileocolonic or colonic disease or SES-CD of 3 for isolated ileal disease.

Subjects with clinical non-response to risankizumab at Week 12 will be re-randomized in a 1:1:1 ratio to risankizumab 1200 mg IV dose group, risankizumab 360 mg SC dose group, or risankizumab 180 mg SC dose group in the Induction Period 2. Subjects with clinical non-response to placebo at Week 12 will blindly receive risankizumab 1200 mg IV dose. No stratification will be made for the Induction Period 2 randomization.

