For the corresponding ITT populations, subjects were assigned to a treatment group based on the randomization or re-randomization schedule, regardless of the treatment actually received. The demographics/baseline and efficacy analysis will be based on the corresponding ITT population.

Safety Population

For the safety populations, subjects were assigned to a treatment group based on the treatment actually received. The safety population (SA) consists of all subjects who received at least one dose of study medication. The safety analysis in each induction period will be based on the following safety population.

12-Week Induction Period:

- **SA1:** This safety population for the 12-Week Induction Period consists of all subjects who received at least one dose of study medication from the 12-Week Induction Period.
- **SA1A:** This safety population for the 12-Week Induction Period includes the subjects in SA1 set who had baseline eligible SES-CD of ≥ 6 (≥ 4 for isolated ileal disease).

Induction Period 2:

- **SA2:** This safety population for the Induction Period 2 consists of subjects who received at least one dose of risankizumab during the Induction Period 2.
- **SA2A:** This safety population for the Induction Period 2 includes the subjects in SA2 set who had baseline eligible SES-CD of ≥ 6 (≥ 4 for isolated ileal disease).

All Risankizumab:

- **SA-ALL:** This safety population includes all subjects who received at least one dose of risankizumab any time during the study.

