9.2.2 Adverse Event Overview

An overview of AEs will be presented consisting of the number and percentage of subjects experiencing at least one event for each of the following AE categories:

- Any treatment-emergent AE
- Any treatment-emergent AE related to COVID-19
- Any treatment-emergent AE related to study drug according to the investigator
- Any severe treatment-emergent AE
- Any serious treatment-emergent AE
- Any treatment-emergent AE leading to discontinuation of study drug
- Any treatment-emergent AE leading to death
- Treatment-emergent AEs of Safety Interest including
 - Adjudicated MACE events
 - Serious infections
 - Active Tuberculosis
 - Opportunistic infections excluding tuberculosis and herpes zoster
 - Malignant tumors
 - Malignancies excluding NMSC
 - Hypersensitivity – serious events only
 - Adjudicated anaphylactic reaction
 - Serious anaphylactic reaction
- All deaths
 - Deaths occurring \leq 140 days after last dose of study drug
 - Deaths occurring $>$ 140 days after last dose of study drug
 - Deaths related to COVID-19

The exposure adjusted rate for AE overview will be presented as well.

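### TEAEs are defined by onset only, so unless worsening is recorded as a new event, an AE that begins on placebo and worsens after the Week 12 switch is left out of the risankizumab TEAE tables

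*SAP*

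**What the plan says.** Section 9.2.1 gives three definitions of a treatment-emergent adverse event (TEAE), and each turns on when the event starts.

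- **12-Week Induction Period:** onset from the first dose, with the window closing at the first M16-000 dose, "or until first dose of study drug in Induction Period 2 if the subject is enrolled into Induction Period 2", or 140 days after the last dose if the subject enters neither.
- **Induction Period 2:** "events that begin either on or after the first dose of the study medication in the Induction Period 2".
- **All Risankizumab:** "events that begin either on or after the first dose of risankizumab".

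The two supporting rules in that section also concern onset. One covers an event starting on the day of first dose. The other covers partial dates: "If an incomplete onset date was collected for an adverse event, the event will be assumed to be treatment-emergent", unless other evidence rules this out.

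Section 2.3 sets up the treatment change: "Subjects with clinical non-response to placebo at Week 12 will blindly receive risankizumab 1200 mg IV dose". Section 4.0 places those subjects in SA2 once dosed, and in SA-ALL: "This safety population includes all subjects who received at least one dose of risankizumab any time during the study".

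On severity, Section 9.2 says that "if the same adverse event occurs multiple times within a subject, the highest severity and level of relationship to investigational product will be reported".

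**The concern.** An onset-only rule does little harm in a trial where each subject has one treatment. Here placebo non-responders change to risankizumab within the study, and they are subjects with active disease who may well carry an ongoing event across the change. If such an event is held as one record with a placebo-period start date, its only TEAE classification is the 12-week placebo group, whatever happens to it on risankizumab.

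At stake are the first-exposure safety data in the placebo/risankizumab group and the pooled All Risankizumab summaries. Severe or serious worsening, or worsening that leads to stopping risankizumab, could be missing from tables meant to describe events on the drug.

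**Working it through.** The SAP has no figure to reproduce on this point. The check is whether any rule captures a worsening, followed by an illustration of scale.

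**1. One event traced through the definitions.** Take an AE that starts on placebo at Week 10, is ongoing at Week 12, and becomes serious at Week 16 after the first risankizumab dose. It is held as a single record.

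| Output | Included? | Reason |
|---|---|---|
| 12-week TEAEs, placebo | Yes | Onset precedes the first Induction Period 2 dose |
| Induction Period 2 TEAEs | No | Onset precedes the first Period 2 dose |
| All Risankizumab TEAEs | No | Onset precedes the first risankizumab dose |

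If the event had begun on 12-week *risankizumab*, it would also be missing from the Period 2 tables. It would stay in All Risankizumab, because it began after the first risankizumab dose.

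**2. Which outputs inherit the rule.** The Section 9.2.2 overview rows for severe events, serious events ("Any serious treatment-emergent AE"), events leading to discontinuation, events leading to death, and areas of safety interest are all headed as treatment-emergent. So are the SOC/PT and maximum-severity tables in Section 9.2.3.

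**3. Which outputs are not worded as limited to TEAEs.**
- The separate all-deaths rows in Section 9.2.2.
- The SAE and discontinuation summaries and listings in Section 9.2.5. That section gives no rule for assigning a carried-over event to a period or treatment.
- Laboratory and vital-sign findings. In Induction Period 2 these are measured from a baseline reset before the first risankizumab dose of that period (Section 9.1).

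**4. Denominator.** Section 9.2.4 counts exposure from the first dose in the relevant period or study. A switcher's risankizumab time therefore enters the exposure-adjusted rate, while the worsening of a placebo-onset event is absent from the numerator.

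**5. Severity shown in the 12-week tables.** The rule in Section 9.2 addresses repeat occurrences, not one continuing event that crosses periods. No rule limits a 12-week event to the grade reached before the switch. Under Section 8.1 the 12-week database locks only when all subjects have finished Week 12 or discontinued, so earlier enrollees may already have Period 2 follow-up in their records. A later grade could then appear in a 12-week column. This is an inference from the absence of a limit, and it applies to risankizumab and placebo non-responders alike.

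**6. Scale.** Section 2.4 gives 171 placebo subjects and 342 + 342 = 684 risankizumab subjects. (Section 2.2 lists placebo as 342, but 171 is the figure behind the power statements.) The SAP gives no non-response or AE rates, so the three rates below are assumptions.

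- Placebo non-response and entry to Period 2, 40% to 70%: 171 × 0.40 = 68; 171 × 0.70 = 120.
- An event ongoing at the switch, 20%: 68.4 × 0.20 = 13.7; 119.7 × 0.20 = 23.9.
- Any worsening of that event, 10% to 20%: 13.7 × 0.10 = 1.4; 23.9 × 0.20 = 4.8.

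That is about 1 to 5 subjects. As a share of switchers it is 0.20 × 0.10 = 2% to 0.20 × 0.20 = 4%. As a share of All Risankizumab it is 1.4/(684 + 68) = 0.2% to 4.8/(684 + 120) = 0.6%. These counts cover any worsening; those becoming severe or serious would be fewer.

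**The case against.** The strongest reply is that the SAP is silent on AE recording because that belongs to the protocol or the case report form. If a worsened or newly serious event is entered as a new record with its own onset date, the definitions already count it under risankizumab. This stands, and it is why the point is conditional. It does not remove the point, because the SAP must define attribution across a treatment change and does not say which convention it relies on.

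A reader might infer that such events are *never* counted against risankizumab. The documents do not support that: besides the recording convention, the outputs in step 3 of the working are not worded as TEAE-restricted. In addition, the MACE and adjudicated anaphylaxis categories in Appendix B come from adjudicated terms, and nothing shows that these take the onset date of an earlier AE.

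A reader might also infer that the safety comparison leans towards the drug. That is not shown. The contrast with placebo comes from the 12-week tables, where carry-forward can raise the risankizumab columns as well as the placebo column. A net lean would need different carry-over rates by arm, which the SAP does not give. Every subject in Induction Period 2 receives risankizumab, so omissions there do not distort a placebo contrast.

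**Conclusion.** The point holds in conditional form. Section 9.2.1 is onset-only. If worsening is not recorded as a new event, an AE begun on placebo that worsens or becomes serious after the switch is left out of the Induction Period 2 and All Risankizumab TEAE tables and the TEAE-based overview rows, although the switcher's exposure is counted. An event begun on 12-week risankizumab is missed in Period 2 only.

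For events carried over from placebo, the omission can only lower the risankizumab TEAE counts. The number affected cannot be derived from the SAP and is probably small; the 1 to 5 subjects above rest wholly on assumed rates. No claim about the direction of the 12-week risk differences is supported. The gap is still worth closing, because serious-event counts may themselves be small and the wording is cheap to change.

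**What to change.** In all three definitions in Section 9.2.1, change *begin* to *begin, or worsen in severity or become serious*. State that the worsening is counted in the period and treatment in which it occurs. If the AE form opens a new record on worsening, say so and use that record's date.

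Where dated severity or seriousness is available, report the 12-week tables at the level reached before the first Induction Period 2 dose. If the form stores only the maximum grade, this last step cannot be programmed, and the SAP should state that limitation.

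The cost is SAP wording, some AE programming, and possibly a few more events in the risankizumab columns.
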